8.6. Management of Overdoses, Trial treatment error, or Occupational Exposure

8.6.1. Overdose

Overdose is administration of a quantity of a trial treatment, either per administration or cumulatively, which is in excess of the protocol specified dose. The dose can either be evaluated as overdose by the trial team at site or by the Sponsor upon review.

There is no or little information on overdose with pembrolizumab or rituximab. In case of overdose, patients must be closely monitored for signs or symptoms of adverse reactions and appropriate symptomatic treatment instituted.

Overdoses should be reported on an incident report (see section 13.1). Any adverse events resulting from an overdose should be reported as a SAE (see section 12.2.2 for reporting procedures). Overdoses of pembrolizumab that are in excess of 5 x the protocol specified dose (i.e. >1000 mg), with or without adverse events resulting from an overdose, should be reported as an adverse event of special interest (AESI) (see section 12.1 and 12.4, Adverse event of special interest, for reporting procedures).

8.6.2. Medication error

A medication error is any unintentional error in prescribing, dispensing, or administration of an IMP or an investigational treatment while in the control of a healthcare professional or consumer. The error can be identified either by the trial team at site or by the Sponsor upon review.

If the medication error is an overdose, refer to the section above. Otherwise, medication errors should be reported on an incident report (see section 13.1). Any adverse events resulting from a medication error/investigational treatment error should be reported as an SAE (see section 12.2.2 for reporting procedures).

8.6.3. Occupational exposure

Exposure to an IMP as a result of one's professional or non-professional occupation. Occupational exposure should be reported on an incident report form (see section 13.1).

8.7. Supportive Care

Supportive Treatment

Patients should receive appropriate supportive care as deemed necessary by the treating investigator. The following supportive treatments are recommended:

- Tumour lysis syndrome medication (e.g. allopurinol*) daily for 7 days starting 24-48 hours prior to trial treatment (first cycle only)
* rasburicase can be used as per local policy
- Antiviral prophylaxis (e.g. aciclovir) for the duration of treatment and for 3 months after completion
- PCP prophylaxis: Local PCP prophylaxis policy should be followed
- Moderate anti-emetic risk: Local anti-emetic policy should be followed

Suggested supportive care measures for the management of adverse events with potential immunologic aetiology are outlined above (section 8.4). Where appropriate, these guidelines include the use of oral or intravenous treatment with corticosteroids as well as additional anti-inflammatory agents if symptoms do not improve with administration of corticosteroids. Note that several courses of steroid tapering may be necessary as symptoms may worsen when the steroid dose is decreased. For each disorder, attempts should be made to rule out other causes such infection, which might require additional supportive care. The use of corticosteroids as supportive care for any other indication, such as anti-emetic therapy, during study is not permitted (see section 8.8 below).

G-CSF/transfusions may be given prior to treatment (including during screening) at the discretion of the local investigator as per local practice.

Concomitant Medication

Concomitant medication may be given as medically indicated at the local investigator's discretion.

Viral Hepatitis

Serious or life-threatening reactivation of viral hepatitis may occur in subjects treated with rituximab. Therefore, subjects who are anti-HB core positive, or have a known history of HBV infection, should receive prophylaxis as per local policy.

Vaccines

Even though no interaction studies have been performed, patients are permitted to receive COVID-19 vaccinations that are not live vaccines during treatment. The timing of COVID-19 vaccine administration and trial treatment should be determined by the Principal Investigator or a Co-investigator at site in the best interests of the patient, however it is recommended patients should not receive pembrolizumab within 24 hours of having a COVID-19 vaccine. Details of vaccine administration should be added to the Rolling Concomitant Medication CRF and medical records.

Administration of inactivated (killed antigen) vaccines is permitted.

8.8. Contraindications

The use of topical or systemic corticosteroids or immunosuppressants should be avoided during the trial (except in the case of immune-related toxicity - see sections 8.4) because of their potential interference with the pharmacodynamic activity and efficacy of pembrolizumab. If possible, patients should stop any steroid treatment prior to study entry. If, however, this is not possible, patients will be permitted to enter the trial if the dose of steroids is at a low dose (≤ 10 mg/day prednisolone or equivalent corticosteroid) which has been stable for at least 3 months. Unless due to immune-related toxicity, the initiation of steroid treatment during the study, or the necessity to increase the dose of any ongoing steroid treatment, should lead to withdrawal of the patient from the study.

Participants are prohibited from receiving the following therapies during treatment:

- Antineoplastic systemic chemotherapy or biological therapy
- Immunotherapy not specified in this protocol
- Chemotherapy not specified in this protocol
- Investigational agents other than pembrolizumab
- Radiation therapy
 - Note: Radiation therapy to a symptomatic solitary lesion or to the brain may be allowed at the investigator's discretion.
- Live vaccines within 30 days prior to the first dose of study treatment, while participating in the study, and for 4 months after stopping treatment. Examples of live vaccines include, but are not limited to, the following: measles, mumps, rubella, varicella/zoster, yellow fever, rabies, BCG, and typhoid vaccine. Seasonal influenza vaccines for injection are generally killed virus vaccines and are allowed; however, intranasal influenza vaccines (e.g. FluMist®) are live attenuated vaccines and are not allowed.

- Systemic corticosteroids for any purpose other than to modulate symptoms from an event of clinical interest of suspected immunologic etiology. The use of physiologic doses of corticosteroids may be approved after consultation with the Sponsor.

Participants who, in the assessment by the Investigator, require the use of any of the aforementioned treatments for clinical management should be removed from the study. All treatments that the Investigator considers necessary for a participant's welfare may be administered at the discretion of the Investigator in keeping with the community standards of medical care.

Medications or vaccinations specifically prohibited in the exclusion criteria are not allowed during the ongoing study. If there is a clinical indication for any medication or vaccination specifically prohibited during the study, discontinuation from study therapy or vaccination may be required. The final decision on any supportive therapy or vaccination rests with the Investigator. However, the decision to continue the participant on study treatment requires the mutual agreement of the Investigator, the Sponsor and the participant.

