8.11. Clinical Management after Treatment Discontinuation

After treatment discontinuation, further therapy will be at the discretion of the treating clinician. Subsequent treatment will not be considered part of the trial.

If a patient discontinues trial treatment early, they will remain on trial for follow up purposes unless they explicitly withdraw consent. Also refer to sections 9 (Assessments) and 15 (Withdrawal of Patients) for further details regarding treatment discontinuation, patient withdrawal from trial treatment and withdrawal of consent to data collection.

For all patients, disease status, late toxicity and survival will be followed up yearly until the last patient completes 2 years of follow up and the end of trial is declared.

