9.4. Assessments after treatment discontinuation (for reasons other than disease progression)

If patients complete treatment or are withdrawn from trial treatment early, for reasons other than disease progression the following assessments are to be performed on day 60 (+/- 3 days) following treatment discontinuation:

- Clinical examination: physical examination (including assessment of lymph node, liver and spleen size)
- Concurrent medication assessment
- Adverse event assessment
- Blood pressure
- Weight
- Assessment of ECOG performance status (see appendix 3)
- Full blood count (including red blood cell (RBC), haemoglobin (Hb), white blood cell (WBC) absolute neutrophil count (ANC), absolute lymphocyte count (ALC), haematocrit and platelets)
- Biochemistry (including bicarbonate, uric acid, albumin, alkaline phosphatase (ALP), alanine/aspartate transaminase (ALT/AST), total bilirubin, calcium, creatinine, potassium, sodium, glucose, urea, and estimated glomerular filtration rate (eGFR), U&E, liver function tests (LFT), LDH, and amylase)
- TSH, glucose and ACTH tests

Patients will then be assessed at 5 months (+4 weeks) after the date of treatment discontinuation, over the phone or at a standard hospital visit for the purposes of:

- Adverse event assessment

Patients are then followed up for the trial annually from the date of treatment discontinuation for the following:

- Remission status assessment (investigations as per local protocols)

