15.1. Patients who do not start Trial Treatment

If a patient does not start treatment, the reasons for this must be recorded in the patient's medical notes and on the relevant Case Report Form(s). Reasons that a patient may not start treatment include:

- Deterioration in health
- Patient decision
- No longer eligible

If a patient does not start treatment, then the patient should be withdrawn from the trial. Data collected will be used in the trial analysis, where appropriate. Biological samples collected may still be used unless the patient explicitly withdraws consent to this.

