15.2. Discontinuation of Trial Treatment

A patient may be withdrawn from trial treatment whenever such treatment is no longer in the patient's best interests, but the reasons for doing so must be recorded in the patient's medical notes and on the relevant Case Report Form(s). Reasons for discontinuing treatment may include:

- Disease progression whilst on therapy
- Unacceptable toxicity (see section 8.5 for full details)
- Intercurrent illness which prevents further treatment
- Patient decision not to continue with trial treatment
- Any alterations in the patient's condition which justifies the discontinuation of treatment in the site investigator's opinion
- Non-compliance with the trial treatment and/or procedures
- If a female patient becomes pregnant or male/female fails to use adequate birth control (for patients of childbearing potential)

In these cases patients will remain within the trial for the purposes of follow-up and data analysis unless they explicitly withdraw consent. See section 9 for details.

If a patient expresses their wish to withdraw from trial treatment, sites should explain the importance of remaining on trial follow-up, or failing this of allowing routine follow-up data to be used for trial purposes and for allowing existing collected data to be used. If the patient gives a reason for wishing to discontinue treatment, this should be recorded.

The following CRFs should be submitted if a patient discontinues trial treatment early:

- Treatment summary form
- Treatment forms for all cycles of treatment received
- Rolling AE form for all cycles of treatment received

Thereafter, unless the patient has withdrawn consent, the site should report AEs/SAEs and submit relevant follow up forms.

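### Section 8.8 says patients needing non-immune steroids or prohibited therapy should leave the study; 8.5, 8.11, 9.4 and 15.2 keep patients who stop treatment in follow-up

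*Combined protocol and SAP*

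**What the plan says.** Section 8.8 contains three statements about patients who need a drug that the protocol restricts.

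- Steroids: unless the reason is immune-related toxicity, starting a steroid or raising an existing dose "should lead to withdrawal of the patient from the study".
- Prohibited therapies: participants who, in the investigator's assessment, "require the use of any of the aforementioned treatments for clinical management should be removed from the study".
- Closing paragraph, on medications and vaccinations barred by the exclusion criteria: "discontinuation from study therapy or vaccination may be required". It adds that a decision to keep the participant on study treatment needs the agreement of investigator, sponsor and participant.

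The sections that govern early stopping of treatment read differently.

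- 8.5: patients who discontinue treatment go on being followed up, with a pointer to 8.11.
- 8.11: "If a patient discontinues trial treatment early, they will remain on trial for follow up purposes unless they explicitly withdraw consent".
- 9.4: for patients who finish treatment or are withdrawn from it early without progression, "the following assessments are to be performed on day 60 (+/- 3 days) following treatment discontinuation". A 5-month contact and yearly follow-up come after that.
- 15.2: "In these cases patients will remain within the trial for the purposes of follow-up and data analysis unless they explicitly withdraw consent". It continues: "Thereafter, unless the patient has withdrawn consent, the site should report AEs/SAEs and submit relevant follow up forms".

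Section 15.1 does use leaving the trial in its full sense, but only for the untreated: "If a patient does not start treatment, then the patient should be withdrawn from the trial".

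**The concern.** The first two statements in 8.8 take the patient out of the study; the other sections take the patient off treatment only. No section defines the 8.8 wording as treatment-only, and 8.8 carries no cross-reference to 8.11 or 15.2. It is also the section a site will open when a patient needs a steroid.

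The patient at stake has been treated, has not progressed, and needs a steroid or another restricted therapy for clinical reasons. If follow-up stopped there, the analyses in 17.2.2 would censor PFS and OS at the date last seen. Time to next treatment would be censored in the same way, unless a new line had already started, which is an event. The two scheduled contacts in 9.4 would not take place. This would be a route out of follow-up that section 15 does not otherwise offer to a treated patient, since there follow-up ends only through withdrawal of consent or loss.

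**Working it through.** The plan gives no figure on this point, so the check is mainly a comparison of texts.

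**1. Can 8.8 be read as treatment-only?** Elsewhere the protocol usually names treatment when it means treatment. Sections 8.2 and 8.4.6 speak of ceasing study therapy, and 8.4.3 of discontinuing study drug. Section 15 separates patients who never start (15.1, out of the trial) from those who stop (15.2, still followed). Against that, 6.3.5 runs withdrawal from the trial and from further treatment together for pregnancy, so usage is not uniform. The treatment-only reading is plausible but not stated.

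**2. Do the follow-up rules exempt these patients?** No. 8.11 covers any early stop. The list of reasons in 15.2 is open-ended and includes changes in the patient's condition that justify stopping. 9.4 covers every reason other than progression. All of these apply to the patient whom 8.8 would remove.

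**3. Is 8.8 consistent with itself?** No. Its closing paragraph treats stopping therapy as something that may be needed and leaves room to continue by agreement. The two sentences before it say the patient should leave the study.

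**4. Who is affected?** Immune-related steroid use is exempt. Physiologic steroid doses may be approved after consulting the sponsor. Radiation to a symptomatic solitary lesion or to the brain may be allowed. Progressed patients are covered by 9.3 and by progression reporting in 12.5. The remaining group is narrow.

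**5. What would be lost for one such patient?** Inputs: minimum follow-up 2 years from registration (section 1.1), taken as 104 weeks; 3-week cycles, at most 18 (8.2), so cycle 18 day 1 falls 17 × 3 = 51 weeks after cycle 1 day 1 if nothing is delayed. Assumptions: treatment starts at registration, the removal week is hypothetical, and nothing is recovered from records or registries. Follow-up given up after removal at week w is (104 − w)/104:

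- w = 12: 92/104 = 88%
- w = 24: 80/104 = 77%
- w = 51: 53/104 = 51%

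These figures illustrate one patient and do not estimate an effect on the trial. Under 8.4.1 cycles are delayed rather than omitted, so the last dose can fall later than week 51. Removal during undelayed treatment falls before the 2-year landmark for PFS and OS. One patient is 1/42 = 2.4% of the planned sample.

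**6. Safety data.** The day-60 and 5-month contacts in 9.4 would be missed. The duty to record AEs and report SAEs to 5 months after the last dose (12.2.1, 12.2.2) is tied to dosing, not to those visits.

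**The case against.** The strongest reply is that 8.8 uses study loosely for study treatment and that the rest of the protocol settles the matter. Follow-up after stopping treatment is stated in 8.5, 8.11, 9.4 and 15.2. Section 15 is the designated place for withdrawal rules, and the end of 8.8 uses treatment-level language. The verb in 8.8 is should, so it does not strictly order removal. Many sites would probably follow 15.2. All of this stands, and it keeps the point minor. It does not make the text consistent: 8.8 states a rule, and that rule differs from the other four sections.

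Outcomes might also be recovered. Section 11 collects the NHS/CHI number for registry follow-up, and 15.4 asks sites to re-contact lost patients or check records before the primary analysis. This helps in part. 15.4 is written for patients lost to follow-up, not for patients removed under 8.8, and the documents do not say that registries would supply progression dates.

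On safety, the objection largely succeeds. A reader might infer that safety reporting ends with removal. The documents do not support that: besides 12.2.1 and 12.2.2, section 15.3.2 keeps SAE reports coming even from patients who refuse all further data collection. What is at risk is the two scheduled contacts, not the reporting duty.

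**Conclusion.** Wrong as written, and minor. Two sentences in 8.8 contradict 8.5, 8.11, 9.4, 15.2 and the closing paragraph of 8.8 itself. The consequence depends on a site following 8.8 literally and on outcomes not being recovered by other means. The number of patients is not stated and is probably small.

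Two stronger readings are not supported.

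- A reader might infer a loss of power or a distorted primary endpoint. Any such calculation needs an assumed number of removals. The missing-data table in 17.2.1 already classifies a patient with no week-24 response, in either direction depending on earlier response and clinical status. The day-60 list in 9.4 includes no IgM measurement, so keeping the patient in follow-up under 9.4 would not by itself supply a week-24 response.
- A reader might infer that PFS would be biased by informative censoring. That is possible. However, 8.8 gives only a concern that steroids may interfere with pembrolizumab's activity, and the documents show no link between such drug use and progression.

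**What to change.** In both sentences of 8.8, replace withdrawal or removal from the study with: *discontinuation of trial treatment, unless continuation is agreed as described at the end of this section; follow-up continues per sections 8.5, 8.11, 9.4 and 15.2*. The clause on agreed continuation is needed because a flat instruction to stop treatment would still clash with the closing paragraph. The cost is two phrases, with no new data, visits or patients.

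Two separate wording corrections belong in the same amendment but add no weight to this point:

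- Exempt the glucocorticoid premedication for rituximab, suggested in 8.3.5, from the steroid bans and the withdrawal rule in 8.7 and 8.8. As written, neither section excepts it.
- Add to the exceptions in exclusion criterion 25 (section 6.2.2) the steroid dose of at most 10 mg/day prednisolone or equivalent, stable for at least 3 months, that 8.8 permits at entry.

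Each takes about one clause per section.

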8.9. Pharmacy Responsibilities

All pharmacy aspects of the trial at participating sites are the responsibility of the PI, who may delegate this responsibility to the local pharmacist or other appropriately qualified personnel, who will be the Pharmacy Lead. The delegation of duties must be recorded on the site staff delegation log.

Pembrolizumab supplied for the PembroWM trial are for PembroWM trial patients only and must not be used outside the context of this protocol.

Pharmacists should refer to the Summary of Drug Arrangements document for further details on suppliers, ordering, labelling, storage, preparation and handling and destruction.

8.9.1. Temperature Excursions

All temperature excursions outside the storage conditions specified in the IB/Summary of Drug Arrangements document must be reported to UCL CTC as per the 'Pharmacy Procedure for Reporting Temperature Excursions' (see Pharmacy Site File).

Upon identifying an excursion:

- all affected trial stock must be quarantined IMMEDIATELY
- the 'Notification of Temperature Excursion' form must be completed and e-mailed to [contact] or faxed to [name].

Please note that UCL CTC must be informed immediately if a patient has been administered drug affected by a temperature excursion.

8.9.2. IMP accountability

The Pharmacy Lead must ensure that appropriate records are maintained.

These records must include accountability for each drug including: receipt (where applicable), dispensing, reconciliation and destruction of unused medication (on sponsor authorisation). Accountability forms will be supplied, and must be used, unless there is a prior agreement from UCL CTC to use alternative in-house records.

Copies of completed drug accountability logs must be submitted to UCL CTC for all trial patients upon request. Also refer to section 14.2 (Centralised Monitoring).

8.10. 24 Hour/Out-of-Office Hours Emergency Drug-Specific Advice

Pembrolizumab	Office hours	All other times
	09:00 to 17:00 Monday to Friday, excluding Bank Holidays	Outside office hours
	Contact UCL CTC [name]	Merck Sharp & Dohme Ltd Switchboard: [name]

8.11. Clinical Management after Treatment Discontinuation

After treatment discontinuation, further therapy will be at the discretion of the treating clinician. Subsequent treatment will not be considered part of the trial.

If a patient discontinues trial treatment early, they will remain on trial for follow up purposes unless they explicitly withdraw consent. Also refer to sections 9 (Assessments) and 15 (Withdrawal of Patients) for further details regarding treatment discontinuation, patient withdrawal from trial treatment and withdrawal of consent to data collection.

For all patients, disease status, late toxicity and survival will be followed up yearly until the last patient completes 2 years of follow up and the end of trial is declared.

8.12. Drug Provision after the End of the Trial

Patients will receive pembrolizumab for a maximum of 1 year or until disease progression, treatment discontinuation due to unacceptable toxicity, or any other reason (whichever occurs sooner). There are no arrangements in place for supply following progression or beyond a year of treatment.

